Obstructive Sleep Apnea Syndrome (OSAS) is a very common disorder with a high prevalence in the general population. Common manifestations of OSAS include snoring, excessive daytime sleepiness, fatigue as well as long term sequelae like memory loss and attention deficits¹, hypertension, arrhythmias, coronary artery disease², congestive heart failure, stroke³ and insulin resistance⁴. Given the significant impact of OSAS on overall health and quality of life, it is very important to treat it optimally. The treatment of OSAS most commonly involves the use of Continuous Positive Airway Pressure (CPAP) to maintain patency of the upper airway. Nonadherence rates to CPAP are variable and range from 29% to 83%⁵⁻⁷ in various studies. One of the common reasons for non-compliance with CPAP usage is mouth dryness⁸. Mouth dryness or xerostomia also impairs sleep quality and overall quality of life⁹ and can be further exacerbated in patients who are mouth-breathers or have underlying conditions predisposing to xerostomia. Anecdotally, in our clinical experience, approximately 80%-90% patients with OSAS on CPAP therapy complain of dry mouth. In about 1/3rd of these patients, the sensation of mouth dryness is significant and bothersome enough to decrease compliance with CPAP. The addition of heated humidification may improve the mouth dryness but has a variable impact on CPAP compliance with some recent studies showing no improvement in CPAP compliance at all⁹. Given the significant adverse effects of OSAS on health, alternative measures to improve CPAP compliance in patients with OSAS need to be considered and evaluated. . As part of this initiative, our study aims to show improvement in patient CPAP compliance with the use of NeutraSal, a supersaturated calcium phosphate rinse, targeted at treating the dry mouth associated with CPAP therapy.

Study Trial (Post-market)

NeutraSal in the Management of Xerostomia in Obstructive Sleep Apnea Syndrome patients utilizing CPAP therapy

Study Population:

Patients are male or female, ages 18-84, with a diagnosis of obstructive sleep apnea syndrome (OSAS), who have been started on CPAP treatment and have subsequently complained of dry mouth or developed worsening of a pre-existing dry mouth condition, as an effect of CPAP treatment.

Study Design:

Randomized, double- blinded, study of OSAS patients undergoing CPAP therapy designed to observe the impact of NeutraSal on compliance to CPAP therapy as compared to placebo.

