Patients will complete an oral questionnaire on the state of xerostomia since the initial visit and compliance with CPAP therapy will be reviewed by history and by objective CPAP compliance downloads. Researchers will also review the patient diary for compliance to dosing for medication. CPAP compliance will be recorded as the number of days that the patient used CPAP for ≥ 4 hours/day and the average number of hours of nightly usage. CPAP compliance downloads are provided by durable medical company (DME) providers and usually indicate both of these measures. The dates between which the compliance is measured are also indicated on the compliance downloads provided by the DME providers. CPAP compliance will be recorded on the 2nd visit at 6 weeks and the 3rd visit at 12 weeks. Every effort will be made to obtain CPAP compliance from the date that subjects are started on neurasal/placebo until the dates of the study visits. If CPAP compliance for the entire period of 6 weeks before the 2nd visit and 3 months before the 3rd visit is not available, then any compliance data from a point after subjects received the study drug till a date in the 5-7 week period around visit 2 and in the 10-12 week period around visit 3 will be recorded. The date range of the available compliance data will also be recorded.

If any patients miss follow-up visits, then phone follow-up will be done to obtain information about their product utilization, compliance to dosing and xerostomia symptom relief. CPAP compliance downloads for these patients will be obtained from the DME providers.

Adverse Event Reporting:

Adverse Event (AEs) and Serious Adverse Event (SAEs) will be reported immediately, if suspected to be related to treatment.

Subject Withdrawals:

Subjects will be advised that they are free to withdraw from the study at any time for any reason, or, if necessary, the Investigators may withdraw a subject from the study, according to the following criteria, to protect the subject's health:

- Intolerable adverse effects
- Major violation of study protocol procedures
- Non-compliance with protocol
- Subject unwilling to proceed or consent is withdrawn
- Pregnancy

Statistical Analysis Plan:

This is a double-blind, randomized, intention to treat, controlled clinical trial comparing Neurasal to Sodium Chloride placebo in a 1:1 randomization. The primary analysis is a comparison of CPAP compliance measured by days CPAP was used for ≥ 4 hours per night over 12 weeks.

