The secondary analyses include:

1)CPAP compliance as measured by average number of hours of daily CPAP use.

- 2) improvement in the total score of the Xerostomia questionnaire measured at baseline and 12 weeks.
- 3) Change in resting salivary pH between baseline and 12 weeks.

Statistical analysis will be performed using two sided t-test with $p < 0.1$ being considered significant for this pilot study. Missing data will be treated by use of last data carried forward methodology.

Sample size determination

This is a pilot study in which there are no previous data to determine an accurate sample size that would definitively prove or exclude the possibility of a treatment effect. We estimate the treatment to be effective at improving CPAP compliance in 25% of subjects. This would translate to the same estimated increase in number of days in which CPAP is used for ≥ 4 hours. Therefore, a sample size of 30 subjects is needed to obtain an 80% confidence level with a response rate of 25%. We estimate that 2 subjects will drop out, therefore we will need 32 subjects for this study.

Informed Consent Process:

The language and writing of an informed consent will be at a 6th grade level. No potentially vulnerable subjects will be enrolled in the study, such as, pregnant and lactating women, children, prisoners, cognitively impaired and critically ill subjects.

Privacy and confidentiality:

Human subjects' names will be kept on a password protected database, and will be linked only with a study identification number for this research. There will be no patient identifiers. All data will be entered into a computer and kept on password protected network storage. Hard copies of the records collected as a part of this study will be kept in a locked office. Only the study personnel will have access to the study records.

Risk/Benefit:

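### The plan has no rule for a CPAP report that ends between weeks 7 and 10 or for a known CPAP stop, so the carried-forward week-6 value is wrong: too high for average hours, and in an undefined direction for the primary day count

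*Combined protocol and SAP*

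**What the plan says.** All references are to the combined protocol and SAP.

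- **Endpoints (Statistical Analysis Plan).** "The primary analysis is a comparison of CPAP compliance measured by days CPAP was used for" at least 4 hours per night, over 12 weeks. This is a count, and no denominator is given. The first secondary analysis is "CPAP compliance as measured by average number of hours of daily CPAP use".
- **Intended data (Follow Up Visits).** The aim is a CPAP record that runs from the first use of product up to each visit. For missed visits, downloads are still to be requested from the equipment (DME) provider.
- **Fallback (Follow Up Visits).** The condition for it reads: "If CPAP compliance for the entire period of 6 weeks before the 2nd visit and 3 months before the 3rd visit is not available". In that case, data from after the subject received product "till a date in the 5-7 week period around visit 2 and in the 10-12 week period around visit 3 will be recorded". The dates that the download spans are kept as well.
- **Missing data (Statistical Analysis Plan).** "Missing data will be treated by use of last data carried forward methodology". This is the only rule. It does not say whether a count of days or a nightly rate is carried.

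No section says how nights after a CPAP stop enter the analysis, or what happens to a download that ends between the two windows.

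**The concern.** The trial asks whether a rinse improves CPAP compliance, and its introduction cites nonadherence of 29% to 83%. Stopping CPAP is therefore a foreseeable value of the outcome. After a known stop, use is zero rather than unknown.

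The two fallback windows leave a gap. Suppose a subject's report ends in week 8 or 9, for example because CPAP was stopped and the device no longer reports. That report is not recorded for visit 3. Observed nights after week 6 are lost, and the week-6 value is carried forward as the 12-week result. The same rule applies to a subject who is still on CPAP but whose report was cut short, and nothing in the analysis separates the two.

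The unstated scale is also at stake. With 16 subjects per arm, choosing between a carried count and a carried rate after seeing the data could move the primary result in either direction.

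**Working it through.** The plan gives no usage figures, so it has no figure of its own to reproduce on this point. The usage rates and stop times below are assumptions.

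**Inputs from the document:** 12 weeks = 84 nights; visit 2 at 6 weeks = 42 nights; 16 subjects per arm (Sample Size); fallback windows of weeks 5-7 and 10-12.

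**Assumed:** 5.0 h/night until the stop; 30 qualifying nights in the first 42 (5 per week), at the same rate until the stop; CPAP stop and end of report at week 8 or 9; visit-2 download ending at week 6.

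**Average hours (secondary).** True 12-week mean = 5.0 × (stop week)/12. The carried value is 5.0 h.

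| Stop | True mean | Excess | Excess/16 (one subject) | Three subjects in one arm |
|---|---|---|---|---|
| Week 8 | 5.0 × 8/12 = 3.33 h | 1.67 h | 0.10 h | 0.31 h |
| Week 9 | 5.0 × 9/12 = 3.75 h | 1.25 h | 0.08 h | 0.23 h |

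At the edges of the gap, weeks 7 and 10, the true means are 2.92 h and 4.17 h. The carried value is too high throughout.

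**Days with at least 4 h (primary).** True count = (30/42) × nights until the stop. A carried count is 30. A carried rate gives (30/42) × 84 = 60.

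| Stop | True count | Carried count: error | Carried rate: error |
|---|---|---|---|
| Week 8 (56 nights) | 40 | 30 − 40 = −10 | 60 − 40 = +20 |
| Week 9 (63 nights) | 45 | 30 − 45 = −15 | 60 − 45 = +15 |

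Per subject in a 16-subject arm mean, the week-8 errors are −10/16 = −0.625 days and +20/16 = +1.25 days. Over 3 to 6 qualifying nights per week and stops from week 7 to week 10, a carried count is 3 to 24 days too low and a carried rate 6 to 30 days too high.

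**A continuing user whose report is cut short** at the same rate has a true count of 60. A carried count gives 30; a carried rate gives 60. A raw count is therefore unsuitable here too.

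**Check of the remedy, stop at week 9.** Days: 45 observed + 0 over the last 21 nights = 45 of 84. Hours: (63 × 5.0 + 21 × 0)/84 = 3.75 h. Both match the truth.

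**The case against.** **Stopping CPAP does not in itself make data missing.** This stands. Downloads are sought up to each visit date, and from the DME provider when a visit is missed. A subject who stops but whose device still reports has observed nights of non-use. A reader might infer that the plan treats every CPAP abandoner as missing; the text does not say so. The problem needs the report itself to end in the gap, and the documents give no frequency for that. The cited 29% to 83% is general nonadherence, and the plan's only attrition estimate is 2 of 32 subjects.

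**The primary endpoint is a count.** This also stands. A reader might infer that stopping is scored as continued use on the primary endpoint, so that placebo is flattered and the comparison pulled towards no difference. That follows for average hours, or for days carried as a rate, if more subjects stop on placebo. If the raw count is carried, those subjects lose real days and the difference is widened instead.

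**A larger figure is easy to produce.** A stop exactly at week 6 gives a true mean of 2.5 h against 5.0 h carried, or 2.5/16 = 0.16 h per subject. That case does not involve the gap between the windows, so it does not measure this problem.

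**Some information on stopping is collected.** Compliance is also reviewed by history, and the download's date range is kept. The data collection forms were submitted to the IRB and are not in the document, so a stop-date field may exist. However, the listed content of the phone follow-up covers product use, dosing compliance and xerostomia relief, not CPAP stopping, and no analysis rule uses the date range.

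**Conclusion.** The concern holds in a limited form. Taken literally, the fallback windows and the single carry-forward rule discard observed data for a report ending between weeks 7 and 10 and put a wrong 12-week value in its place.

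- For average hours the error is upward: about 0.10 h (stop at week 8) or 0.08 h (week 9) per affected subject in a 16-subject arm mean, at an assumed 5 h/night.
- For the primary day count the direction is undefined. In the week-9 example the true value is 45, and the plan's wording permits 30 or 60.

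The gap, the sole carry-forward rule and the missing scale are facts of the text. The size rests on assumed usage and stop times, and the overall effect depends on how many reports end in the gap, which the documents do not let us estimate. The plan should be corrected, but the documents do not show that the trial's result is biased in a known direction.

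**What to change.** 1. Use every post-randomisation download up to day 84, whatever its end date, including those that end between the two windows.
2. At each visit or call, record whether and when CPAP was stopped, unless the forms already capture this.
3. State in the SAP that nights after a documented CPAP stop, up to day 84, count as 0 h and not as qualifying days, and that hours are averaged over all nights to day 84.
4. Limit carry-forward to subjects still using CPAP whose report could not be obtained. State the scale: carry the nightly rate over the uncovered nights, not the raw count.

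The cost is SAP wording and at most one data field, with no extra visits or subjects. The small downside is that a stop date may rest on the subject's or DME provider's report. The wording should be fixed before the data are unblinded, so that the scale is not chosen with the results in view.

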Sample Size

~32 patients per site (16 in study group and 16 in placebo group)

Population

The population will be composed of patients with a confirmed diagnosis of OSAS who are on CPAP therapy, have developed new onset of dry mouth or have worsening of pre-existing dry mouth condition, as an effect of CPAP treatment, meet the other inclusion criteria and do not have any exclusion criteria.

Trial Duration

Ongoing recruitment; subjects will be followed for 12 weeks from the time of enrollment in the study.

Trial Agent and Intervention Description (If applicable)

NeutraSal, dosed 2 times per day at waking and bedtime (indications 2-10 times per day or PRN), swish and spit, daily for a term of 12 weeks.

Primary Objective

To observe the impact of NeutraSal on OSAS patients compliance to CPAP therapy compared to placebo.

Secondary Objective

To assess whether the daily use of NeutraSal will prevent or reduce dry mouth perception in patients undergoing CPAP therapy

Tertiary Objective

To assess whether NeutraSal will balance the pH of the oral mucosa long term (3 months)

Efficacy Measurements:

1. Compliance with use of cpap
2. Xerostomia Questionnaire
3. Resting Saliva pH Testing
4. Product Utilization based on Patient Diary

Exit Evaluation:

1. Brief Physical Exam for Overall Health
2. Final collection of patient information during visit on data form
3. Final review of efficacy measurements

Study Population:**Inclusion /Exclusion Criteria**

The inclusion criteria will be as follows:

1. Patient should be above 18 years of age.
2. Patients who have been initiated on CPAP therapy after an initial diagnosis of OSAS and have developed dry mouth or have worsening of pre-existing dry mouth condition, as an effect of CPAP therapy.
3. Ability to attend visits at the research site
4. Patient should be able to read and/or understand and sign the consent form be willing to participate in the research study

The exclusion criteria are as follows:

1. Patients with open mouth sores at study entry.
2. Any pathology that, based on the judgement of the researcher, could negatively affect the oral mucosa and subsequent treatment for xerostomia (immune disorders, etc.)
3. Patients using any other prophylactic mouthwashes.
4. Patients who are pregnant and/or nursing.
5. Patients becoming pregnant during the treatment period will be removed from data.
6. Patients on a low sodium diet
7. Patients currently on medication or treatment for xerostomia

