- Product Utilization and Compliance to Dosing (Patient Diary Reviewed)
- Adverse Effects
- Resting salivary pH

Schedule of Study Events:

	Baseline Visit	6 Weeks	12 Weeks
Medical History	X		
Brief Physical Exam	X	X	X
Pregnancy Test	X	X	X
Informed Consent Form	X		
Inclusion/Exclusion Criteria	X		
Treatment Administration	X	X	X
Xerostomia Questionnaire	X	X	X
Resting pH	X	X	X
Compliance Report/ Patient Diary	X	X	X
Adverse Effect Monitoring	X	X	X

Data collection instruments are included in the IRB submission.

Screening Visit/ Initial Visit

During this visit, OSAS patients on CPAP who are eligible for study enrollment will be given information about the study. An informed consent form will be reviewed and signed. Subjects will receive a brief physical medical exam and a baseline visual examination of the oral mucosa. Once enrolled in the research study, patients will receive either medication or placebo in a randomized selection. Patients will also complete an oral questionnaire on the state of xerostomia. Researchers will do a baseline pH test of the oral mucosa. Patients will be

instructed on proper use of neurasal or placebo. Patients will be given a diary or questionnaire to record compliance to the product and Xerostomia symptom relief.

Follow Up Visits

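### Xerostomia score and salivary pH are to be tested as change scores by t-test; ANCOVA on the baseline already collected is usually more precise, at little cost

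*Combined protocol and SAP*

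**What the plan says.** The Statistical Analysis Plan section of the combined protocol and SAP lists two secondary analyses that compare baseline with 12 weeks: "improvement in the total score of the Xerostomia questionnaire measured at baseline and 12 weeks" and "Change in resting salivary pH between baseline and 12 weeks". One sentence gives the method for every analysis: "Statistical analysis will be performed using two sided t-test with $p < 0.1$ being considered significant for this pilot study". No ANCOVA, regression model or covariate is named anywhere in the document.

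Both measures are taken before follow-up starts. Under Screening Visit/ Initial Visit: "Patients will also complete an oral questionnaire on the state of xerostomia" and "Researchers will do a baseline pH test of the oral mucosa". The Schedule of Study Events table marks the questionnaire and resting pH at baseline, 6 weeks and 12 weeks.

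The two analyses serve the Secondary Objective ("To assess whether the daily use of NeutraSal will prevent or reduce dry mouth perception in patients undergoing CPAP therapy") and the Tertiary Objective, on long-term oral pH.

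**The concern.** Subtracting the baseline is itself an adjustment, but with the slope fixed at 1. If patients with a high baseline score tend to fall back towards the mean, the true slope is below 1 and subtraction over-corrects. Part of any chance baseline difference between arms then stays in the estimated treatment effect. It does so as random error, which the t-test's standard error already reflects, and not as bias. ANCOVA estimates the slope from the data and removes that part.

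With 16 per arm precision is scarce, and the covariate is already being collected. These are the only listed tests of dry mouth perception and oral pH. Relief of dry mouth is also the route by which the protocol expects CPAP compliance to improve, so it is worth estimating well.

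**Working it through.** **Inputs from the documents.** 16 per arm, N = 32 (Sample Size); 1:1 allocation and two-sided significance at p < 0.1 (Statistical Analysis Plan). No SD, correlation, effect size or power is stated for either outcome, so there is no figure in the plan to reproduce.

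**Assumed.** Correlation r between baseline and 12 weeks of 0.3 to 0.8, and k = SD at 12 weeks / SD at baseline of 0.8, 1 or 1.25. The slope of the 12-week value on baseline is rk. The t-test is read as two-sample, between arms; the plan does not say paired or unpaired, but describes a comparison with placebo.

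**Formulas** (variance of the treatment difference, up to a common factor):

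- Change-score t-test: 1 + k² − 2rk
- ANCOVA: k²(1 − r²) × (1 + 1/(N − 4)). The last factor is the small-sample cost of estimating the slope: 1 + 1/28 = 1.036.

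Since 1 + k² − 2rk = k²(1 − r²) + (1 − rk)², the change score carries an excess of (1 − slope)² times the baseline variance. That excess is never negative. ANCOVA can therefore lose at most the factor 1.036, and does so only when the slope is exactly 1.

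**Ratio of ANCOVA variance to change-score variance, N = 32**

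| | r = 0.3 | r = 0.5 | r = 0.7 | r = 0.8 |
|---|---|---|---|---|
| k = 1 | 0.673 | 0.777 | 0.880 | 0.932 |
| k = 1.25 | 0.812 | 0.925 | 1.016 | 1.036 |
| k = 0.8 | 0.520 | 0.592 | 0.650 | 0.663 |

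Example, k = 1 and r = 0.5: the change score gives 1 + 1 − 1 = 1; ANCOVA gives 0.75 × 1.036 = 0.777.

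**What the k = 1 row means**

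- Patient equivalent, 1/ratio: 1.49, 1.29, 1.14 and 1.07. At r = 0.5 the change-score test would need about 32 × 1.29 = 41 patients to match ANCOVA with 32.
- Width of the 90% CI (critical t 1.699 on 29 df against 1.697 on 30 df): 0.82, 0.88, 0.94 and 0.97 of the change-score width.
- Break-even: 1.036(1 + r)/2 = 1 gives r = 0.93.
- Illustrative power for an assumed true difference of 0.8 SD, change score against ANCOVA: 59% and 74% at r = 0.3; 71% and 81% at r = 0.5; 89% and 92% at r = 0.7.

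The rows k = 1.25 at r = 0.7 and 0.8 (slopes 0.875 and 1) are small losses of about 2% and 4%. The larger of these is the worst case and widens the 90% CI by about 2%.

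**Baseline imbalance.** Its standard error is √(2/16) = 0.354 baseline SD. What reaches the change-score estimate is |1 − slope| times this. For k = 1 that is 0.25, 0.18, 0.11 and 0.07 SD at r = 0.3, 0.5, 0.7 and 0.8.

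**Checks.** Simulation of 40,000 trials per setting at 16 per arm, k = 1, gave ratios of 0.669, 0.773, 0.877 and 0.930. Type I error at two-sided 0.10 was 0.097 to 0.102 for both methods across all k. If the two expected dropouts leave 15 per arm, the k = 1 ratios are 0.675, 0.779, 0.883 and 0.935 and break-even is r = 0.926.

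**The case against.** The strongest reply is that this is a choice between two valid analyses in a self-declared pilot. The plan names an outcome, a test and a threshold in advance, and nothing in it contradicts that choice. This stands: the point concerns efficiency only.

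Second, the size of the gain rests on values the documents do not give, and over the assumed grid it runs from 48% less variance to about 4% more. Eligibility requires new or worsened dry mouth, which may narrow the baseline spread of the xerostomia score. For a given slope and residual variance, a narrower spread shrinks ANCOVA's advantage. This also stands, and is why no single figure should be taken as the expected gain. It does not reverse the recommendation, because the loss is capped at 3.6% while the possible gain is many times larger.

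Third, the cost is more than one degree of freedom, since the slope must be estimated. That is true, and the factor 1.036 includes it in every ratio above.

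Fourth, moving to the 12-week value could look like a change of endpoint. It is not: with baseline as covariate, ANCOVA on the 12-week value and ANCOVA on the change give the same treatment estimate and standard error. The listed change endpoints can stay.

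**Conclusion.** The concern holds as a recommended improvement. The planned change-score t-test is valid, but ANCOVA on the baseline already collected is more precise over most plausible values. With equal SDs and 16 per arm, variance falls by about 33%, 22%, 12% and 7% at correlations of 0.3, 0.5, 0.7 and 0.8. The advantage disappears at about r = 0.93, or wherever the slope is close to 1, and the loss never exceeds 3.6%.

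This rests on assumed correlations and SD ratios, and on reading the t-test as a comparison between arms. It covers the xerostomia score and salivary pH only. It does not carry over to CPAP compliance, because the Follow Up Visits section records downloads at 6 and 12 weeks and describes no download from before study product.

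**What to change.** Replace the t-test for these two outcomes in the Statistical Analysis Plan section, before unblinding, with:

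> The 12-week xerostomia total score and 12-week resting salivary pH will each be compared between arms by ANCOVA with treatment and the baseline value of the same measure as covariate. The adjusted difference will be reported with its 90% CI. This estimates the same treatment difference as ANCOVA on the change from baseline.

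The last sentence keeps the text consistent with the listed change endpoints, and the 90% interval matches the plan's 0.1 threshold. State also that baseline is measured before the first dose, since the order within the initial visit is not explicit. The initial-visit text refers to pH of the oral mucosa and the SAP to resting salivary pH; confirm that they are the same measurement, so that covariate and outcome match.

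Cost: SAP wording only. No new data or visits, one degree of freedom per model, and at most about 3.6% more variance at N = 32 if the true slope is 1.

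### Carry-forward enters a week-6 day count as a 12-week total: about half the true value for a steady CPAP user with no week-12 download, though few subjects should be affected

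*Combined protocol and SAP*

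**What the plan says.** The Statistical Analysis Plan section of the combined protocol and SAP defines the outcome: "The primary analysis is a comparison of CPAP compliance measured by days CPAP was used for ≥ 4 hours per night over 12 weeks". The Follow Up Visits section gives the timing: "CPAP compliance will be recorded on the 2nd visit at 6 weeks and the 3rd visit at 12 weeks". Each count should ideally run from the start of study product to the visit, so both are cumulative.

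If the full period is not available, the same section accepts "any compliance data from a point after subjects received the study drug" up to an end date "in the 5-7 week period around visit 2 and in the 10-12 week period around visit 3 will be recorded". It adds: "The date range of the available compliance data will also be recorded". No section says that this date range is used in the analysis.

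For subjects who miss visits, the protocol says: "CPAP compliance downloads for these patients will be obtained from the DME providers". The Subject Withdrawals section allows subjects to leave, and it also says that "the Investigators may withdraw a subject from the study". It does not say whether downloads are still obtained for those subjects.

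One missing-data rule covers every outcome: "Missing data will be treated by use of last data carried forward methodology".

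**The concern.** Carrying the last value forward makes sense for a level or a rate, such as mean nightly hours, the xerostomia score or salivary pH. It does not suit a cumulative count, because the week-6 count has had only half as many nights in which to accumulate. Using it as the 12-week value silently assumes that CPAP was never used for 4 hours after week 6.

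A related scale problem arises without any missing data. A visit-3 download that ends at week 10, or starts late, is accepted as the observation, but its count covers fewer than 84 nights and is not corrected.

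At stake is the primary comparison, with 16 subjects per arm. An affected steady user becomes an artificially low value, which adds noise. If the affected subjects fall mostly in one arm, the estimated difference is also shifted.

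**Working it through.** **Plan's own figure.** The documents give no figure for the effect of carry-forward. The nearest is the dropout allowance under Sample size determination: 30 + 2 = 32, which reproduces. It implies 2/32 = 6.25% lost.

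**Inputs from the documents.** 12 weeks = 84 nights; week 6 = 42 nights; accepted end dates in weeks 5-7 and 10-12; 16 per arm; two-sided t-test at 0.10; planned effect 25%. No SD or control-arm day count is given.

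**Coverage of the 84 nights, download starting at product start**

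| Download ends | Nights | Share |
|---|---|---|
| Week 5 | 35 | 42% |
| Week 6 | 42 | 50% |
| Week 7 | 49 | 58% |
| Week 10 | 70 | 83% |

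A late start lowers these shares, and no lower limit is stated. For example, 28 nights would be 28/84 = 33%.

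**Carried count over true count**, at nightly rate r up to week 6:
- steady use: 42r/84r = 50%
- use halves after week 6: 42r/(42r + 21r) = 42/63 = 67%
- use stops at week 6: 42r/42r = 100%

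**Shift in a 16-subject arm mean.** Each week-6-only steady user loses 42r days, so the mean falls by 42r/16. This is 1.3, 1.7 and 2.1 days at assumed r = 0.50, 0.65 and 0.80. A week-10 download gives 14r/16 = 0.6 days at r = 0.65.

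**Two such subjects in one arm.** The difference shifts by 2 × 42r/16 = 2.6, 3.4 and 4.2 days.
- If 25% means percentage points, the effect is 0.25 × 84 = 21 days and the shift is 12.5%, 16% and 20% of it.
- If 25% means a relative increase, the share is 2(42r/16)/(0.25 × 84r) = 25%. It is 31% if the affected subjects use CPAP at the treated rate 1.25r.

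**Simulation.** 100,000 trials per cell, 16 per arm, pooled two-sided t-test at 0.10, steady individual rates (beta or clipped normal). The means and SDs are assumptions and are not in the documents.

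Type I error, mean 65% of nights, SD 15-25 points:

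| Affected subjects | Type I error |
|---|---|
| None, one, or two at random | about 10% |
| One in each arm | 6-8% |
| Two in one arm | 12-14.5% |

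Power, 50% against 68% of nights, SD 20 points:

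| Situation | Power |
|---|---|
| No loss | 79-80% |
| Two at random, carried forward | 74% |
| Two at random, excluded | 77-78% |
| Two at random, rate per covered night | 79-80% |
| One in active arm, carried forward | 69% |
| Two in active arm, carried forward | 56% |
| Two in placebo arm, carried forward | 88-90% |

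The placebo-arm row is not a benefit: there the scale error inflates the apparent effect.

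**The case against.** The strongest reply is that the plan does not say whether the raw count or the compliance level is carried forward. Since date ranges are recorded, an analyst could rescale. That is possible, but nothing says so, and the outcome is defined as a count. The choice should not be left until the data are unblinded.

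Second, few subjects are exposed. Two dropouts are expected, and provider downloads close the main route to a missing week-12 count. This stands and limits the seriousness. It does not extend to partial downloads accepted at visit 3, whose frequency the documents do not indicate.

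Third, the large distortions need both losses in one arm. With two losses at random, the chance that both are in the active arm is (16/32)(15/31) = 24%, and averaged over random loss the type I error is 10%. This also stands, and nothing in the documents predicts loss by arm.

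Fourth, someone lost after week 6 may have stopped CPAP. The carried count is then correct, and a rate would be too high by the same 42r/16 days in the arm mean. This is the real weakness of the remedy, so a sensitivity analysis is needed.

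Finally, visit dates vary and the protocol also describes the last period as 3 months, so even complete counts may not span exactly 84 nights. That is a further reason to define a denominator.

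**Conclusion.** The concern holds and should be fixed. Read literally, the rule gives a steady user without a week-12 download about 50% of the true primary value (42-58% for end dates in weeks 5-7, less with a late start). These ratios follow from the documents' own time points, given steady use. The effects in days rest on assumed nightly rates, and the power and error figures on assumed means and SDs.

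The expected damage is modest: about 5 points of power with two random losses, with type I error unchanged. It is larger if the losses cluster in one arm. Mean nightly hours, xerostomia score and pH do not have this scale error.

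**What to change.** Do not carry the day count forward. State in the SAP:

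- **Retrieval.** Request the provider download from product start to day 84 for every randomised subject, including those withdrawn from product where consent allows.
- **Primary measure.** Analyse days with at least 4 hours of use divided by nights covered by the download. Covered nights without use count as zero. Where the full period is covered, this only rescales the count and leaves the t-test unchanged.
- **Minimum coverage.** Fix it in advance, for example 28 nights, or weight by nights covered. At r = 0.65 with independent nights, the standard error of one subject's rate is √(0.65 × 0.35/28) = 0.09 at 28 nights, against 0.18 at 7.
- **Sensitivity analysis in all randomised subjects.** Score nights from the last covered date to day 84 as non-use, leave nights before a late-starting download out of the denominator, and enter subjects with no download as zero.
- **Reporting.** Give by arm the numbers with partial, below-minimum and no download, and state that the last two groups are absent from the primary rate analysis. Subjects with no on-product download have no count to carry forward under the present rule either.

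The cost is a few sentences and slightly more download retrieval and analysis. The downside is that the rate assumes uncovered nights resemble covered ones; the sensitivity analysis tests this.
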